9.3. Post treatment phase

Clinical assessment and surgery (week 22 to week 24)

This visit will occur once inflammation has subsided at 10-12 weeks after completing treatment (i.e week 22-24). All patients will proceed to surgery irrespective of the amount and frequency of imiquimod used.

Clinical response will be quantified by reference to the pre-treatment clinical photographs and to map 1 by the same observer, and recorded.

Clinical response is categorised as follows:

- Clinical complete regression (CCR) complete disappearance of abnormal pigmentation.
- Clinical partial regression (CPR) reduction in the size of the pigmented area or an obvious reduction in its intensity.
- Clinical No change (CNC) appearance identical to that pre-treatment.
- Clinical progressive disease (CPD) Increased size or increased intensity of pigmentation, or development of a nodule within the LM indicating invasive melanoma.

Before surgery, map 1 will be superimposed on the skin, and the outline positioned over the 4 point tattoos. Map 1 will be drawn on the skin with ink using a 0.5 mm nib surgical marker pen. If there is new pigmentation contiguous with map 1 but outside it, this too will be outlined and recorded (map 2).

A standardised (i.e. same camera, setting and distance) digital clinical photograph will be taken of map 1, and map 1 plus map 2 where appropriate.

One 4 mm punch biopsy will be taken from normal looking skin within map 1. One 4mm punch biopsy will also be taken from any areas of residual pigmentation. In addition, one 4 mm punch biopsy will be taken from pigmentation apparent in map 2.

The area excised will include; the tattoos; the area defined by map 1; the area if any defined by map 2; plus a 5 mm surgical margin of clinically normal skin, and all underlying subcutaneous fat until a deep anatomic margin – either muscle, muscle fascia, periosteum,or perichondrium is reached, or at least 5mm of fat if there is no definable anatomic deep margin. The surgical margin will be marked with normal surgical marking

ink. Excision of both map 1 and 2 is necessary to minimise risk of false positive CR, as it is possible that sub-clinical pre-treatment disease apparent as post-treatment pigmentation may extend beyond the boundaries of map 1. It should be noted that surgery will remove all biopsy and tattoo sites.

The surgical specimen will be orientated, marked at each quadrant, a ligature put at 12 o'clock and placed in formalin. The specimen must sit flat in the formalin filled container, and a screw top or specialised leak proof container must be used. Along with the biopsies and the surgical specimen, 1 H&E (with three levels) stained slide from the initial diagnostic biopsy along with the corresponding histopathology report will be sent to the study histopathologist. The specimens will be transported by same-day courier to the address below.

FAO: [name] LIMIT-1 Study Histopathology Department The Royal Surrey County Hospital NHS Trust [name]

[contact] [contact]

Please contact the Histopathology Department at The Royal Surrey County Hospital to let them know when to expect arrival of specimens.

The gross appearance of the specimen will be recorded with a digital photograph so that the orientation of the specimen, biopsies, and subsequent pathological sections can be related. Sections will be cut at 2 mm intervals throughout the whole specimen and examined by the study histopathologist and characterised as either:

- Pathological complete regression (PCR) absence of LM in all biopsies and excision specimen
- Pathological partial regression (PPR) atypical melanocytes are present in the epidermis, and are of abnormal distribution and number, but without sufficient features to define LM in either biopsies, or excision specimens or both
- Pathological no change (PNC) presence of LM in either biopsies or excision specimens, or both
- Pathological progressive disease (PPD) presence of invasive melanoma in biopsies, excision specimens, or both

This will determine the predictive value of the clinical appearance and the biopsy pathology compared with the excision pathology. If the clinical or biopsy results give significant numbers of false negatives, imiquimod is unlikely to have a future in the management of LM. The histopathologist will complete a histopathology report for the participant and send to sites within 2 weeks of surgery.

Post-surgery follow up

There will be two post surgery follow up visits at 1-2 weeks and at 12 weeks after surgery. The patient will be asked to complete the User Opinion Questionnaire at the 12 week post surgery visit.

The histopathology report will be available to the local investigator by two weeks following surgery. If histopathology shows residual LM at a surgical margin, or if invasive melanoma has been found in the biopsies or excision specimen, further treatment will be at the discretion of the patient and treating team.

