Given these potential advantages, imiquimod is increasingly being used off label by dermatologists in the UK. There have been several recent reports of topical treatment with imiquimod (8-14). Whilst the evidence for efficacy is striking with response rates of 77-90% being reported, our own unreported observations suggest that significant numbers may not respond to treatment, and published response rates may reflect reporting bias (15). There is no systematic evidence-base from clinical trials to support this use and so the place of this new treatment requires definition before it becomes firmly embedded in clinical practice (16-19). If it is shown to be safe and effective, understanding the mechanism of action could have major significance for the future management of other types of melanoma.

The results of this study will allow recommendations to be made regarding the use of imiquimod for LM and inform the need for a further definitive randomised trial. A low cure rate or residual sub-clinical disease which could allow LMM to develop undetected would mean a recommendation that imiquimod should not be used as a primary treatment for LM. However, if imiquimod is effective and safe, it is likely to have a role in the management of LM and further research would be warranted. A definitive randomised controlled trial would compare imiquimod with surgery to define CR duration. This approach depends critically on this method of assessment of CR being accurate; this is assessed in this trial. Furthermore, a positive outcome from this study may lead to evaluation of imiquimod as a treatment for other types of melanoma. If the two approaches were equivalent for long term cure of LM, use of imiquimod for LM might spare the majority of patients from surgery and reduce NHS resource use.

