9.1. Pre-study phase

Diagnosis

Diagnosis of LM will be confirmed following biopsy by a specialist skin histopathologist and by clinico-pathological correlation. The biopsy will be one or more 4mm punch biopsies(s) from the darkest area. Surplus diagnostic material (1 H&E stained slide with three levels) will be required by the study histopathologist. This diagnostic slide will be sent by same day courier to the study histopathologist along with the post treatment specimens. The appropriateness of surgery will be confirmed by case review by a skin cancer multi-disciplinary team meeting. The patient will then be given the diagnosis of LM, a pre-check for eligibility will be made and, if appropriate, the study will be explained and the patient offered the chance to participate. Patients will then be given the study patient information leaflet to take home and read.

Baseline visit (week -1)

The patient will be given the opportunity to have a further discussion about the study and receive answers to any questions they may have. The patient will give their written informed consent to take part in the study. The investigator will confirm that the patient is eligible to enter the study, a medical history will be taken and demographic data collected. Before treatment is started, the patient's General Practitioner will be contacted to inform them about their patient's involvement with study, details of the study and the potential local toxicity of imiquimod.

The area of skin involved in the LM will be defined by using temporary surgical skin marking ink, and small point tattoos on the outline of the lesion at 4 sites on its periphery at 12, 3, 6 and 9 o'clock, using established methods for defining radiotherapy treatment sites. The size of the LM will be measured in mm using the largest diameter and its perpendicular. The map will be made under adequate artificial lighting and standardised magnification. The outline of the lesion will be traced onto a transparent sheet, known as 'map 1'. Therefore, map 1 defines the pre-treatment lesion.

A standardised (i.e. same camera, setting and distance) digital clinical photograph of the outlined lesion will be taken as a baseline, pre-treatment reference.

Blood samples will be taken before treatment starts and after the treatment finishes to find out if the imiquimod treatment has resulted in an immune response. Some of the blood taken at this visit is also used for HLA typing.

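### Section 9.3 does not ensure that the post-treatment biopsies are read before, or blind to, the excision they are meant to predict

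*Protocol*

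**What the plan says.** Section 9.3 sets the comparison: "This will determine the predictive value of the clinical appearance and the biopsy pathology compared with the excision pathology". Section 6 explains why it matters for a later randomised trial: "This approach depends critically on this method of assessment of CR being accurate; this is assessed in this trial". Section 15.2 calls knowledge of this accuracy essential. Section 9.3 adds that significant numbers of false negatives would make a future for imiquimod in lentigo maligna (LM) unlikely.

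The same section describes the specimens and their handling:

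- **Sampling.** The punches are chosen by appearance. "One 4 mm punch biopsy will be taken from normal looking skin within map 1"; further punches come from any residual pigmentation and from pigmentation in map 2.
- **Shipment.** "Along with the biopsies and the surgical specimen, 1 H&E (with three levels) stained slide from the initial diagnostic biopsy" goes to the study histopathologist with its report. Section 9.1 agrees: "This diagnostic slide will be sent by same day courier to the study histopathologist along with the post treatment specimens".
- **Reader.** "Sections will be cut at 2 mm intervals throughout the whole specimen and examined by the study histopathologist". No second reader is named.
- **Linkage.** The gross specimen is photographed "so that the orientation of the specimen, biopsies, and subsequent pathological sections can be related".
- **Classification.** Complete regression is "absence of LM in all biopsies and excision specimen". The other three categories are likewise defined over biopsies and excision together.

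No section sets an order of reading, a masked reading or a separate biopsy result. The synopsis gives none under randomisation and blinding.

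**The concern.** A predictive value is interpretable only if the test result was reached without knowledge of the reference. Here one role holds both, and the only categories to be recorded combine them. The line between partial regression and no change is a matter of judgement: abnormal melanocytes are present, and the reader decides whether they amount to LM. A reader who already knows that the excision contains LM may call a borderline punch positive. One who knows that the excision is clear may call it negative. Both shifts raise agreement, and the first removes a false negative, the result that the protocol treats as a warning sign.

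In practice, a patient given imiquimod in place of surgery would have no excision to inform the biopsy reading. Accuracy measured with that knowledge would be too favourable for the intended use. No later analysis can restore independence once the readings have been made.

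**Working it through.** **1. The design figure.** Section 16.1 gives 33 patients and success at 25 or more complete regressions, for 60% against 85%. The exact binomial gives P(X ≥ 25 | n = 33, p = 0.60) = 0.0444 and P(X ≥ 25 | n = 33, p = 0.85) = 0.9505. The stated 5% and 95% are reproduced. This point does not depend on them; only n = 33 and the two rates are used below.

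**2. What the text fixes and what it leaves open.** Sections 9.1 and 9.3 fix joint receipt by one role and joint classification. They do not say in what order the slides are examined. A biopsy-first reading would comply with the text, and so would a reading with the excision already known. The exact statement is therefore that blind biopsy reading is not ensured.

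**3. Weight of one call.** Sensitivity is the number of residual cases with a positive biopsy divided by the number of residual cases. Every patient without complete regression is counted as residual.

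- At a complete regression rate of 85%: 33 × 0.15 = 4.95, about 5 cases. One call is 1/5 = 20 points.
- At 60%: 33 × 0.40 = 13.2, about 13 cases. One call is 1/13 = 7.7 points.

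**4. Two upgraded calls (assumed).** Take 33 − 25 = 8 residual cases, the number at the decision boundary. A blind result of 5/8 is 63% (exact 95% CI 24% to 91%). Two upgrades give 7/8, or 88% (47% to 100%).

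**5. Range over the share upgraded (assumed).** Let s be the true sensitivity and f the share of missed biopsies turned positive by knowledge of the excision, with no false positives. Then observed sensitivity = s + (1 − s)f, false negatives FN = cases × (1 − s)(1 − f), and negative predictive value (NPV) = TN/(TN + FN), with TN = 33 − cases. For 8 cases and s = 50%:

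| f | Sensitivity | FN | NPV |
|---|---|---|---|
| 0 | 50% | 4.0 | 86.2% |
| 10% | 55% | 3.6 | 87.4% |
| 25% | 62.5% | 3.0 | 89.3% |
| 50% | 75% | 2.0 | 92.6% |

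Across 5 to 13 cases and s from 50% to 70%, f = 25% lifts sensitivity by 7.5 points (0.30 × 0.25) to 12.5 points (0.50 × 0.25). NPV rises by about 1 point (94.9% to 96.1% with 5 cases, s = 70%) to 5 points (75.5% to 80.4% with 13 cases, s = 50%).

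**6. Limit on f.** Only a missed biopsy that contains borderline changes can be re-called. A punch that simply did not sample the disease stays negative. So f cannot exceed the borderline share of the missed biopsies, which the protocol does not give and which could be zero.

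**The case against.** The strongest reply is that the protocol never says the biopsies and excision are read together. It describes one consignment and a joint final category. The punches precede the excision, and a sequential reading fits the text. The photograph is for orientation; nothing says the biopsy call is made from it. This stands, and a reader who infers that the histopathologist reads everything at once goes beyond the document.

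A reader might also infer that unmasked reading would hide the false negatives wholesale. It would not. A single 4 mm punch from normal-looking skin can miss disease elsewhere, and no knowledge of the excision changes such a slide. Downgrading after a clear excision removes false positives, not false negatives. The intervals in step 4 overlap widely, so the trial could hardly tell the two results apart.

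A third inference is that the number and site of the punches give away the clinical response and must be masked. The number can hint at residual pigmentation but does not identify the full clinical category, and it stays visible whatever is done. Section 15.2 treats examination and biopsy as a combined assessment, so knowing the biopsy site is not clearly a fault.

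Finally, the consequence is bounded. The primary outcome is by definition a joint classification of all tissue, section 16.1 keeps the secondary outcomes subordinate, and section 16.2 reports them descriptively. Section 19.2 mentions study SOPs, which are not shown and might set a reading order. That possibility does not answer the point: section 9.3 already fixes shipment, sectioning, reader and categories, and it offers no biopsy-only result that an SOP could protect.

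**Conclusion.** The point holds as a gap in safeguards. Section 9.3 does not ensure that the biopsy result is independent of the excision result it is to predict, and it defines no biopsy-only result. Borderline calls could drift towards the excision, inflating agreement and understating false negatives in the secondary accuracy outcome.

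Each upgraded call is worth about 8 to 20 points of sensitivity, given 33 evaluable patients and a complete regression rate between 60% and 85%. The number of calls that would change is unknown; the scenarios in the working are assumptions, and no effect at all is possible.

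The documents do not support a claim that the primary result or the 25/33 rule is compromised, or that joint reading is prescribed. The change should be made because it is cheap beforehand and impossible to make good afterwards.

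**What to change.** State in section 9.3 that:

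1. The study histopathologist reads the post-treatment punch biopsies first, without the recorded clinical response category.
2. A biopsy-only category is entered and locked in the eCRF before the excision sections are examined.
3. The excision is then read and an excision-only category recorded.
4. Relating the biopsies to the specimen, and assigning the combined category for the primary outcome, come last.

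Withholding the biopsy site is not required. Reader, slides, sample size and the two-week report to sites stay as they are. The cost is a fixed reading order for the laboratory and one or two extra eCRF fields. Separate categories without the lock would not be enough, because one informed reader could still assign both.

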9.4. Extra visits

Participants will be encouraged to call the investigator if they are experiencing problems and an unscheduled visit will be arranged if required. Toxicity requiring discontinuing imiquimod treatment will mandate an unscheduled visit so that the dose reduction algorithm can be implemented

The same procedures as for weeks 1-8 will be carried out. However, if the participant wishes to stop imiquimod treatment and so the unscheduled visit becomes the final treatment phase visit, a standardised (i.e. same camera, setting and distance) digital clinical photograph of the lesion will be taken. Imiquimod treatment will be stopped at this point.

10. Study Treatment

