9.2. Treatment phase

Week 0

The date of the first application of imiquimod will be day 1, week 0. Day 1 will be a Monday to facilitate adherence; imiquimod will be applied Monday to Friday with no treatment on Saturday and Sunday. The co-ordinating centre will ensure the investigator is aware of this date as this becomes the reference point for scheduling subsequent treatment phase visits.

Participants will be instructed to apply imiquimod for 12 weeks to the lesion plus a 20 mm margin of surrounding normal skin.

Participants will be asked to keep a study diary during the treatment phase (starting from day 1, week 0) and to bring to each clinic visit to be used as an aide memoir during the consultation. The following information will be recorded in the diary:

- Whether participants have applied imiquimod
- If not whether this was a scheduled day off, or missed due to toxicity .
- The response to "How acceptable have you found the imiquimod treatment over the past week?" answered on a 10cm visual analogue scale ranging from totally acceptable to totally unacceptable
- The name of any topical treatment used on the LM other than imiquimod
- If any of the following adverse reactions have occured:
 - Local reactions redness, swelling, discomfort or pain at the site of application
- There will be space for participants to record anything else they feel is important or that they would like to discuss with the investigator.

Weeks 1, 2, 4 and 8

Scheduled clinic visits will be at 1, 2, 4, 8 weeks after the start of treatment. At these visits, the following will be recorded:

- The contents of the patient daily diary will be reviewed and checked for completeness, and a new diary issued
- The investigator will rate the local site reaction on the following scale:
 - o **none**

- o mild reaction (slight redness, discomfort, no swelling, no ulceration)
- o moderate reaction (redness, pain and swelling, no ulceration)
- o severe reaction (redness, pain, swelling and ulceration)
- The participant will be specifically asked about any flu like symptoms they have experienced since the last visit. If present, these will be documented on the AE eCRF.
- The dose of imiquimod will be adjusted according to the following algorithm:

If intolerable at 5 days per week; stop completely for 1 week then restart but at a reduced dose of 3 days per week. Increase to 5 days per week as soon as tolerable.

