If intolerable at 3 days per week, a further week off, start again at 3 days per week. Stop if intolerable.

If 5 days per week is tolerated increase to 7 days per week. If intolerable repeat algorithm as before.

• Any other new medication usage and health service usage data will be recorded using the diary as an aide memoir.

If treatment of the LM with imiquimod is stopped because of local toxicity, this will prompt an unscheduled clinic visit so that the dose adjustment algorithm can be implemented.

If at any point during the treatment phase, the lentigo maligna is judged to have progressed to invasive melanoma then the patient will progress immediately to surgery. Simple enlargment of the LM macular area does not count as progression to invasive melanoma.

Week 12

At this final scheduled treatment phase visit, the following will be recorded:

- Adverse reaction data at the application site will be recorded from the participant diary and discussion with the participant. The investigator will rate the local site reaction on the following scale:
 - o **none**
 - o mild reaction (slight redness, discomfort, no swelling, no ulceration)
 - o moderate reaction (redness, pain and swelling, no ulceration)
 - o severe reaction (redness, pain, swelling and ulceration)
- Imiquimod treatment will stop at this point.
- The participant will be specifically asked about any flu like symptoms they have experienced since the last visit. If present, these will be documented on the AE eCRF.
- Any new medication usage and health service usage data will be recorded using the diary as an aide memoir.
- All unused medication will be returned and quantified.
- The final diary will be collected.

At this visit the post-treatment blood sample for the immune response is taken, 50ml sodium heparin tube, and is sent by same day courier to the scientific study centre in Birmingham at the address below (refer to section 13 for further details).

[name] Wellcome Trust Clinical Research Facility (WTCRF) University Hospitals Birmingham NHS Foundation Trust Queen Elizabeth Hospital, [name]

[contact]

The investigator site should inform the WTCRF that a sample is to be taken, giving 48 hours notice preferably. Samples should not be sent on a Friday if possible.

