15.2. Secondary Outcome Measures

- Clinical assessment of response after imiquimod treatment:
 - Assessment of clinical response based on examination and presurgical biopsies
 - Pathological assessment of residual LM outside the clinically mapped margins of disease
 - Accuracy of map 1 and map 2 and 5mm surgical margin in predicting complete excision of lentigo maligna

The pathological response in the entire resected lesion will be compared with that predicted from clinical examination and biopsies taken before surgery, post imiquimod treatment. We will assess whether adequate surgical margins can be determined using clinical maps. It is essential to know the accuracy of the method of clinical assessment of response.

- Clinical feasibility of imiquimod treatment:
 - Number of reported local adverse reactions and systemic adverse reactions. These will be collected from the patient held diary and assessment by the investigator
 - o Adherence to treatment schedule
 - Acceptability of imiquimod treatment. This will be collected by a visual analogue scale completed weekly by the participant.
 - o Number and reasons for withdrawal from imiquimod treatment
- Number of consultations with NHS staff during imiquimod treatment
- Frequency of functional T cell responses recognising peptide epitopes in melanocyte differentiation and cancer-testis antigens.

Circulating immune responses to proteins expressed within melanoma will be measured using blood draws taken before imiquimod treatment and after completion of imiquimod therapy but before surgery. The demonstration of a circulating immune response would be an important finding that would strongly support the investigation of imiquimod as primary therapy for melanoma, even if coupled with subsequent surgery because of the potential for such an immune response to be preventative against recurrence or invasive disease.

 Measurement of hypothetical treatment preferences for surgery or imiquimod for LM using standard gamble technique.

The clinical significance of the findings of this trial were pre-determined by consultation with UK dermatologists. This small scale trial will be used to enable patients to actively contribute to the interpretation of results and design of clinical guidelines or a randomised controlled trial.

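### Participants who stop imiquimod early are assigned no visit at which the post-treatment immune blood sample is taken

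*Protocol*

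**What the plan says.** The immune outcome compares blood taken before and after imiquimod. Section 4.1 and the schedule of assessments place the two draws at baseline and week 12. Section 9.2, under Week 12, repeats this: "At this visit the post-treatment blood sample for the immune response is taken, 50ml sodium heparin tube".

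Two other places describe the second draw by its relation to treatment, not by week. Section 9.1 puts it after treatment has finished. Section 15.2 describes "blood draws taken before imiquimod treatment and after completion of imiquimod therapy but before surgery".

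Section 9.4 covers unscheduled visits. Its general rule is "The same procedures as for weeks 1-8 will be carried out". When a participant decides to stop, "the unscheduled visit becomes the final treatment phase visit", and a standardised photograph is added. Nothing else is added.

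Section 10.7 keeps early stoppers in the analysis without replacement. It sends them to surgery, if they agree, at least 12 weeks after the first application and at least 10 weeks after the last. It notes that this secures the primary outcome at least, and says nothing about blood.

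**The concern.** Section 9.4 considers what must be added when treatment ends early, and it names one item. A site that follows it will photograph the lesion, stop the drug and send no blood to the laboratory. Section 13 has each patient's pre- and post-treatment samples run in the same assay, so a participant without the second sample has no paired result.

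Early stopping is a planned path in this trial: the dosing algorithm can end in a permanent stop, and section 10.7 lists the reasons. The people missing from the paired set would therefore be defined by how treatment went, and need not resemble those who completed it. Section 6 describes imiquimod as an immune response modifier that acts through inflammation, so a link between stopping for a reaction and immune response is plausible, though not shown. Section 15.2 treats a circulating immune response as a strong argument for further work, and section 16.1 lets secondary outcomes bear on the decision about a randomised trial.

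**Working it through.** **The plan's own figure.** The protocol gives no number for this outcome. Its one design figure is the primary rule in section 16.1: 33 evaluable patients and at least 25 complete regressions, for rates of 60% against 85%. Exact binomial tails reproduce it:
- P(X ≥ 25 | n = 33, p = 0.60) = 0.0444
- P(X ≥ 25 | n = 33, p = 0.85) = 0.9505

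The target of 40 implies an attrition allowance of 1 − 33/40 = 17.5%. That is not an early-stopping rate: under section 10.7, early stoppers who go to surgery remain evaluable for the primary outcome.

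**Step 1: trace the visits.**

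| Visit | Section | Post-treatment immune blood listed? |
|---|---|---|
| Weeks 1, 2, 4, 8 | 9.2 | No: diary, local reaction, flu-like symptoms, dose adjustment, medication and health service use |
| Unscheduled visit that ends treatment | 9.4 | No: as above, plus a photograph |
| Week 12 | 4.1, schedule table, 9.2 | Yes, 50 ml |
| Clinical assessment before surgery | 9.3 | No: clinical response, maps, photograph, biopsies |
| 1–2 and 12 weeks after surgery | 9.3 | No, and too late for the definition in 15.2 |

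An early stopper's path runs through every row except week 12, whose place as last treatment visit the unscheduled visit has taken. Participants with suspected invasive progression go straight to surgery (9.2, 10.7), and no draw is assigned to them either. The only row with the sample is the one that early stoppers skip.

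**Step 2: count the pairs at stake.** Pairs lost = 40 × f, where f is the proportion who stop early without a sample. The documents give no value for f; 10% to 30% is an assumption.

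| f (assumed) | Pairs lost | Pairs left of 40 |
|---|---|---|
| 10% | 40 × 0.10 = 4 | 36 |
| 20% | 40 × 0.20 = 8 | 32 |
| 30% | 40 × 0.30 = 12 | 28 |

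These counts are before any other loss.

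**Step 3: what this could do to the reported frequency.** Let p_c be the response frequency in completers and p_s that in early stoppers.
- Frequency in everyone: (1 − f) × p_c + f × p_s
- Frequency reported from pairs: p_c
- Shortfall: f × (p_s − p_c)

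The documents give neither f nor p_s − p_c, not even its sign. As arithmetic only: with f between 0.10 and 0.30, a difference of 10 percentage points in either direction moves the result by 1 to 3 points in that direction. This is not an estimate for the trial.

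**The case against.** The strongest reply is that nothing forbids the sample. Sections 9.1 and 15.2 call for blood after treatment and before surgery, and section 10.7 leaves at least 10 weeks between last application and surgery for most early stoppers. A careful site could draw it at the stopping visit, at a retained week 12 visit or before surgery. That stands: the sample is unassigned, and the loss is what follows if sites do only what the visit sections list.

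It also stands that the outcome is secondary and descriptive (section 16.2), and that adding early stoppers' samples mixes shorter exposures and different intervals since the last dose with week-12 samples.

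A reader might infer more than the text supports:
- *That 9.4 and 15.2 contradict each other.* They do not. Section 15.2 leaves room for a draw that 9.4 fails to schedule.
- *That sachet counts are lost too*, because "All unused medication will be returned and quantified" appears under week 12. Section 10.4 requires unused sachets to be recorded, and sections 10.5 and 14.3 require unused supplies to be returned, none of them tied to a visit.
- *That diary data are lost.* Review of the diary is one of the week 1–8 procedures that 9.4 carries over.
- *That early stoppers leave mainly because of toxicity.* Section 10.7 lists four reasons without frequencies, and the algorithm uses breaks and reduced frequency before a permanent stop.
- *That the response frequency will be understated.* The sign of any difference is unknown.

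**Conclusion.** The point holds as a gap in scheduling. As written, no visit before surgery is assigned the post-treatment immune sample for participants who stop imiquimod early, so they have no paired ELIspot result, although the definitions in sections 9.1 and 15.2 would include them. Under an assumed stopping rate of 10% to 30%, this costs 4 to 12 of 40 pairs. The loss may be informative; the size and direction of any bias cannot be known from the protocol. The primary outcome and the 25 out of 33 rule are unaffected.

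Severity is minor. It is still worth correcting now, because which visit carries a blood draw is a protocol matter and no analysis plan can recover a sample that was never taken.

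**What to change.** In section 9.4, and as a note to the schedule of assessments, state that when an unscheduled visit becomes the last treatment visit, the 50 ml post-treatment sample is taken then. If the courier or the laboratory's preferred notice (48 hours, avoiding Fridays) does not allow this, it is taken at a later visit before surgery. The same wording should cover participants who go straight to surgery, without affecting the timing of that surgery. Where no sample can be taken, or consent for it is withdrawn, record the reason.

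For each second sample, record weeks of imiquimod exposure and weeks since the last application. Report ELIspot results for all participants with a pair, and separately for those sampled at week 12 after completing treatment.

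The cost is a sentence and a table note. The sample, packaging and courier are already planned for every participant. The downside is that exposure and sample timing will vary among early stoppers, which is why the completers should also be shown on their own.
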